7.4 Evaluations during the Follow up phase

Follow-up assessments will terminate 2 years after the last patient has completed end of treatment (incl. biopsy, if patient agrees to participate in translational study).

- Evaluation of toxicity
- Treatment outcome
- Endoscopic ultrasound (optional)
Tumor Assessment (CT/MRI chest and abdomen)

7.5 Evaluation of Efficacy

7.5.1 Tumor assessment

Assessment of tumor response will be evaluated using the international criteria proposed by the RECIST (Response Evaluation Criteria in Solid Tumors) committee (New response evaluation criteria in solid tumours: Revised RECIST guideline (version 1.1), Eisenhauer EA et al., Eur J Cancer 2009, see Appendix 4 for further reference).

Only subjects with measurable disease may be enrolled into this study. Measurable disease requires the presence of at least one measurable lesion. Imaging, CT- or MRI-scan, of chest and abdomen must be performed at baseline (within 28 days before start of treatment) for eligibility and also to establish a baseline tumor assessment.

The same method of assessment and the same technique should be used to characterize the reported lesion at baseline and during the following tumor assessments. A switch from CT- to MRI-scan is considered the only acceptable change in modality and should not preclude response assessment if, in the judgment of the radiologist, there is no significant difference in the assessment by CT- and MRI-scan.

CT- and MRI-scan are the best currently available and most reproducible methods of measuring index lesions selected for response assessment. CT- or MRI-scans of the chest and abdomen anatomies are required at baseline. Thereafter, at each imaging time point, a chest CT- or MRI-scan and abdomen CT-or MRI scan are required. CT- or MRI-scans of the chest and abdomen are required at the Final Tumor Assessment visit.

The CT- or MRI-scans should be performed with spiral technique using a 5 mm or less contiguous reconstruction algorithm. Non-spiral CT is also allowed with a recommended reconstruction algorithm or slice thickness of 10 mm or less. Intravenous and oral contrast should be administered if it is not contraindicated. At baseline, tumor lesions will be

categorised measurable if the minimum size is 10 mm (if CT scans are performed at 5 mm slice thickness or less). If CT scans at slice thickness greater than 5 mm are used, the minimum size of measurable lesions at baseline should be twice the slice thickness of the baseline scans.

The lesion will be assessed with imaging with the same method as at baseline and at the end of treatment to monitor progression of disease. Furthermore, at the end of treatment visit, the investigator will exclude symptomatic deterioration suggestive of progression of disease (e.g. a decrease in Karnofsky performance status, metastases). If progression of disease is suspected for any reason during the treatment phase, radiological confirmation is necessary and a new scan must be performed unless a scan taken no more than 14 days earlier is available.

Resectability / Response Criteria per Time Point:

Resectability of the primary tumor and the lymph nodes will be assessed by a surgeon after 4-4.5 weeks of treatment (see 7.2.3).

Overall response will be defined according to the RECIST criteria Version 1.1 based on the assessments for target lesions, non-target lesions as well as considering the occurrence of new lesions, and will be assessed at week 5 and at the end of treatment.

Evaluation of target lesions

Complete Response (CR):	Disappearance of all target lesions. Any pathological lymph nodes (whether target or non-target) must have reduction in short axis to < 10 mm.
Partial Response (PR):	At least a 30% decrease in the sum of diameters of target lesions, taking as reference the baseline sum diameters.
Progressive Disease (PD):	At least a 20% increase in the sum of diameters of target lesions, taking as reference the smallest sum on study (this includes the baseline sum if that is the smallest on study). In addition to the relative increase of 20%, the sum must also demonstrate an absolute increase of at least 5 mm. (Note: the appearance of one or more new lesions is also considered progression).
Stable Disease (SD):	Neither sufficient shrinkage to qualify for PR nor sufficient increase to qualify for PD, taking as reference the smallest sum diameters while on study

Evaluation of non-target lesions

Complete Response (CR):	Disappearance of all non-target lesions and normalization of tumor marker level. All lymph nodes must be non-pathological in size (< 10 mm short axis)
Non-CR/Non-PD:	Persistence of one or more non-target lesion(s) or/and maintenance of tumor marker level above the normal limits
Progressive Disease (PD):	Unequivocal progression of existing non-target lesions. (Note: the appearance of one or more new lesions is also considered progression).

Evaluation of best overall response

The best overall response is the best response recorded from the start of the treatment until disease progression/recurrence (taking as reference for PD the smallest measurements recorded since the treatment started). In general, the patient's best response assignment will depend on the achievement of both measurement and confirmation criteria

Table 9: RECIST 1.1 Evaluation of best overall response

Target lesions	Non-Target lesions	New Lesions	Overall response
CR	CR	No	CR
CR	Non-CR/Non-PR	No	PR
CR	Not evaluated	No	PR
PR	Non-PD or not all evaluated	No	PR
SD	Non-PD or not all evaluated	No	SD
Not all evaluated	Non-PD	No	NE
PD	Any	Yes or No	PD
Any	PD	Yes or No	PD
Any	Any	Yes	PD

7.5.2 Residual tumor classification (R-classification) in patients undergoing surgery

The R-classification will be performed by the pathologist using the resected tumor. The pathologist will determine, if residual tumor is present at the resection lines. The definitive R-classification considers clinical and pathological information and includes the following categories:

- R0 no residual tumor
- R1 microscopic residual tumor
- R2a macroscopic residual tumor, microscopically not confirmed
- R2b macroscopic residual tumor, microscopically confirmed

8 Statistical Considerations

Having fixed the safe dose in our former phase I study (LEOPARD Phase I), 134 patients should be treated at a dose of 1000 mg/m² FU and 20 mg/m² cisplatin to evaluate the 2-year overall survival of the immuno-radiochemotherapy. However, the last patient will be randomized on December 31, 2016 at the latest, which is 2.5 years later than originally planned.

8.1 Analysis set descriptions

Safety Analysis Set

The safety population includes all patients who received at least one dose of trial medication and for whom at least one post-baseline safety measurement is available.

Full Analysis Set

The Full Analysis Set includes all patients who received at least one dose of trial medication and for whom at least one post-baseline efficacy measurement is available.

Per Protocol Set

This population includes all patients with at least six weeks of trial medication plus all patients who discontinued the study prematurely due to lack of efficacy, death or toxicity. Detailed criteria will be defined before analysis.

All safety analyses will be performed on the Safety Analysis Set. For efficacy analysis of the trial, the primary analyses will be based on the per-protocol set. Additional analyses will be performed on the Full Analysis Set for sensitivity purposes.

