7.2.3 Examinations after 4 weeks of treatment

- Endoscopy (incl. biopsy, if patient agrees to participate in translational study)
- Endoscopic ultrasound (optional)
- Tumor assessment (CT/MRI chest and abdomen)
- serum sample (10 ml) for EGFR and ligands determination (if patient agrees to participate in translational study)
- Tissue immunochemistry (if patient agrees to participate in translational study; immunohistochemical blocks should be transported to Mainz for further analysis)
- Re-evaluation by a surgeon with respect to resectability*

**If resectability has been achieved, radiochemotherapy +/- cetuximab is stopped after 45 Gy, and the patient is referred to surgery. If resectability has not been achieved, radiochemotherapy +/- cetuximab is continued as indicated above.*

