8.3.4 Design and assumptions

- Explorative randomized phase II study with 2 parallel groups.
- Primary endpoint: Overall survival rate after 2 years. Survival time will be calculated from time of randomization until death for any reason, or until last date known to be alive, whichever occurs first. In patients without death, the last date known to be alive will be considered as censored survival time.
- The respective experimental therapy arm would be rated as insufficiently active, if the observed OS rate at 2 years is 40 % or lower, as this corresponds to the standard treatment efficacy.
- On the other hand, the experimental therapy would be considered to be a promising candidate for further development (e.g. in a phase III trial), if the true OS rate at 2 years amounted to 45% or more.

- In order to detect potential differences with respect to the investigated study endpoints between female and male gender, subgroup analyses will be performed for both female and male patients. Furthermore, the potential prognostic impact of gender will be analyzed in a univariate and a multivariate manner. Because an adequate statistical power cannot be expected in each of the two subgroups, the statistical evaluation analyses with respect to gender related differences will be presented in a descriptive manner.

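### The primary 2-year survival analysis uses a per-protocol set formed after randomisation; no all-randomised analysis is planned, and the directed stop at 45 Gy is not among the stops kept

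*Combined protocol and SAP*

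**What the plan says.** Section 8.1 defines two efficacy sets and ranks them.

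- **Per-protocol set, primary.** For efficacy, "the primary analyses will be based on the per-protocol set". The first route into the set is by exposure: "This population includes all patients with at least six weeks of trial medication". The second route is by reason for stopping early: "plus all patients who discontinued the study prematurely due to lack of efficacy, death or toxicity". The rest is left open: "Detailed criteria will be defined before analysis".
- **Full Analysis Set (FAS), sensitivity.** It takes patients "who received at least one dose of trial medication and for whom at least one post-baseline efficacy measurement is available". Its role is stated as "Additional analyses will be performed on the Full Analysis Set for sensitivity purposes".

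Section 8 defines no set of all randomised patients. Yet Section 8.3.4 starts the survival clock at randomisation: "Survival time will be calculated from time of randomization until death for any reason". Section 8.4 compares the arms with a log-rank test and a Cox hazard ratio and names no analysis set, so Section 8.1 governs.

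The Synopsis and Sections 5.5 and 7.2.3 direct an early stop for some patients. If the surgeon finds the tumour resectable after 4 to 4.5 weeks, "radiochemotherapy +/- cetuximab is stopped after 45 Gy, and the patient is referred to surgery".

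**The concern.** Membership of the primary set is decided by how long a patient was treated and why treatment ended. Both can depend on the assigned arm in an open-label trial, so the primary comparison is not between the groups that were randomised. Section 8.3.3 justifies randomising on the ground that observed differences should then reflect efficacy and not patient selection. A primary set selected on exposure lets selection back in.

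Two features sharpen this.

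- A patient who becomes resectable and stops at 45 Gy has followed the protocol, but that reason is not on the kept list. Such patients may be removed, and they may differ in prognosis from the rest.
- Withdrawn consent and non-compliance, both withdrawal reasons in Section 4.2.4, are not on the kept list either. Section 5.8 defines insufficient compliance by missed cetuximab infusions, which only arm A receives.

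Deferring the detailed criteria does not remove the problem. The plan does not say they must be fixed before outcomes by arm have been seen, and Section 10 plans an efficacy and futility interim analysis once recruitment stops.

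**Working it through.** **The plan's own counts.** Section 8.4 expects 72–78 patients in the FAS and 66–72 in the per-protocol set. The loss is 72 − 66 = 78 − 72 = 6 patients, or 8.3% to 7.7% of the FAS. The 2 × 33 and 2 × 36 rows of Table 10 match the per-protocol range. Their hazard ratios at 40% control survival reproduce: ln(0.7319)/ln(0.40) = 0.3406 (stated 0.3407) and ln(0.7190)/ln(0.40) = 0.3600 (stated 0.3601). Moving from 66 to 72 patients therefore relaxes the detectable hazard ratio from 0.3407 to 0.3601. Widening the set costs no power by this measure.

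**When does a stop at 45 Gy fall?** Inputs: 1.8 Gy fractions, 5 per week, starting on the first chemotherapy day (Section 5.5.1). That day is day 8 in arm A, with cetuximab from day 1, and day 1 in arm B (Section 4.1). No interruptions are assumed.

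45 / 1.8 = 25 fractions. With a Monday start the 25th falls on day 4 × 7 + 5 = 33 of radiotherapy; with any other weekday start it falls on day 35. Arm A adds 7 days. Arm A has by then had cetuximab on days 1, 8, 15, 22, 29 and 36, that is six weekly infusions.

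| How six weeks is counted | Arm A | Arm B | Who is dropped |
|---|---|---|---|
| 42 days to last fraction, Monday start | day 40 | day 33 | both |
| 42 days to last fraction, other starts | day 42 | day 35 | arm B only |
| 42 days to last drug day | day 39 | day 32 | both |
| Weekly cetuximab infusions in arm A, days in arm B | 6 infusions | day 33 or 35 | arm B only |
| Two chemotherapy courses begun | yes | yes | neither |

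The term is undefined, so the same directed stop can exclude both arms, one arm or neither.

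**Illustrative size.** The documents give no resection rate and no survival after resection. Assumptions:

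- 36 patients per arm, with true 2-year survival p of 40% in arm B and 45% in arm A.
- Resected patients have 2-year survival s of 40–60%. The range is borrowed from Section 2.2, which reports it as a trend in pathologic complete responders and not as a 2-year rate.
- k resected patients are lost from an arm, with the total bounded by the 6 above.

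Per-protocol survival = (36p − ks) / (36 − k).

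| Loss | s = 0.4 | s = 0.5 | s = 0.6 |
|---|---|---|---|
| Arm B, k = 3: rate | 40.0% | 39.1% | 38.2% |
| Difference, arm A intact | 5.0 | 5.9 | 6.8 |
| Arm B, k = 6: rate | 40.0% | 38.0% | 36.0% |
| Difference, arm A intact | 5.0 | 7.0 | 9.0 |
| Arm A, k = 3: rate | 45.5% | 44.5% | 43.6% |
| Difference, k = 3 in each arm | 5.5 | 5.5 | 5.5 |

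For the last row, (16.2 − 14.4)/33 = 5.5 points for any common s.

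Standard errors: one rate, √(0.4 × 0.6/36) = 8.2 points; the difference, √(0.4 × 0.6/36 + 0.45 × 0.55/36) = 11.6 points.

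**The case against.** The case for leaving the plan alone has real content.

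- **Design.** The trial is explorative and sized on evaluable patients. Section 8.3.3 says a strict test between arms is not its purpose. Section 8.4 rests the conclusion on the survival rate with its confidence interval, the reference arm and toxicity. This limits the severity. It does not justify a selected primary set, because valid estimation against the control is the stated aim.
- **The kept list.** Early stops for death, toxicity and inefficacy stay in. That largely avoids the usual bias of a minimum-exposure rule, in which early deaths are lost. This stands.
- **The 45 Gy stop.** A directed stop is arguably not a premature discontinuation of the study, and detailed criteria are still to come. Exclusion is therefore possible, not certain. If only drugs count as medication, both arms fall short by days and that asymmetry disappears. This also stands; it shows that the result hangs on an undefined term.
- **Compliance.** Section 8.1 does not tie the Section 5.8 definition to set membership, and patients who withdraw after six weeks still qualify. That route is secondary.
- **The FAS.** It brings back treated resected patients who have an efficacy measurement. It remains a sensitivity analysis and omits anyone never treated.
- **Size.** The 4.0-point shift needs all six expected losses to be arm B resections, with survival at the top of a borrowed range. Some losses may be withdrawn consent or non-compliance, which would shrink it.

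**Conclusion.** The concern holds. The primary survival analysis is restricted by events after randomisation, no planned analysis includes everyone randomised, and the directed stop at 45 Gy is absent from the kept list.

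Neither the size nor the direction of bias can be derived from the documents. Under the stated assumptions, losses confined to arm B inflate a 5-point difference by up to 4.0 points, and equal losses of 3 per arm add 0.5. All of these shifts are smaller than one standard error, and none takes arm A down to the 40% threshold. The largest is nonetheless close to the 5-point step between 40% and 45% on which the plan's decision rests. The point should be fixed, but it does not by itself undermine the trial.

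**What to change.** Amend Section 8.1 so that the primary 2-year survival analysis covers all randomised patients, in the arm assigned, from the day of randomisation. Keep the per-protocol set and the FAS as sensitivity analyses. Before any comparison of outcomes by arm, define trial medication and its duration in the same way for both arms, and state that a protocol-directed stop at 45 Gy for surgery counts as compliant for the per-protocol set.

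The cost is wording plus some follow-up. Patients never treated would dilute the estimate slightly. Their number is not given, because the 66 in Section 8.4 are patients both randomised and treated. The Synopsis total of 72–78 equals the expected FAS, which suggests few, but the inference is weak: its 33–36 per arm sums to only 66–72. Scheduled follow-up runs from the end-of-treatment assessment (Schedule of Assessments, footnote 8). Vital status for untreated patients must therefore be sought separately, or they are censored at the last date known alive, as Section 8.3.4 already provides.

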8.2 Target variables

8.2.1 Primary variables

For quantification of efficacy the primary objective is the 2-year overall survival.

8.2.2 Secondary variables

- The 1-year overall survival
- The 1-year and 2- year progression-free survival
- The 1-year and 2-year loco-regional control
- The 1-year and 2-year metastases-free survival
- The overall response rate³ (RECIST Version 1.1)
- Toxicity (NCI-CTC 4.0)
- Quality of Life (EORTC QLQ-C30 and QLQ-OES18)

In addition the following parameters will be assessed irrespective of a specific time point:

- OS
- PFS
- MFS

8.3 Statistical analysis

8.3.1 Statistical Methode

Treatment outcome:

Loco-regional control is defined as absence of loco-regional progression based on findings of endoscopy, endoscopic ultrasound, and computed tomography.

OS, PFS, MFS and LC are calculated for both treatment groups and for several potential prognostic factors with the Kaplan-Meier method and measured from the day of randomization .

Such potential prognostic factors are: age (≤ 60 vs. > 60 years), Karnofsky performance status (100%-80% vs. 70%), tumor location (upper third vs. middle third vs. lower third), tumor length (< 7 cm vs. ≥ 7 cm, according to endoscopy), histology (squamous cell carcinoma vs. adenocarcinoma), histologic grade (G1-2 vs. G3), T-stage (T2-3 vs. T4, according to endoscopic ultrasound and computed tomography), N-Stage (N0 vs. N+), and hemoglobin before radiotherapy (< 12 vs. 12-14 vs. > 14 g/dl).

Differences between the Kaplan-Meier curves are evaluated with the log-rank test. Results are considered significant if $P < 0.05$. Potential prognostic factors found to be significant in the univariate analysis, are evaluated in a multivariate analysis performed with the Cox proportional hazard model.

Stratification at randomization according to :

Histology (SCC vs. adeno)

KPS (100%-80% vs. 70%)

Stage (T1-3 N0-1 vs. T4 and/or N2 and/or M1a)

Toxicity:

Both treatment groups are compared for toxicity using the Chi-square test.

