
Sample size calculation and explanation
	
This is an explorative randomized study with 2 parallel groups. Using a standard single-stage phase II design by FLEMING (1981), n = 62 patients evaluable for efficacy have to be recruited. As a similar number of patients is to be recruited to the standard arm, a total number of 124 patients is required. The standard treatment control group serves to reduce some of the result variability which is typically encountered in single-arm phase II trials, especially caused by patient selection phenomena and investigator bias. To cover potentially drop outs 67 patients per arm will be recruited.
 
The OS rate after 2 years is chosen as primary efficacy endpoint. The estimation of the efficacy rate of 40% of the reference group is based on the findings of several studies (Bedenne 2007, Herskovic 1992, Minsky 2002, Stahl 2005, Al-Sarraf 1997, Cooper 1999). Therefore, the respective experimental therapy arm would be rated as insufficiently active, if the observed OS rate at 2 years is 40 % or lower.
 
On the other hand, the experimental therapy would be considered to be a very promising candidate for further development (e.g. in a phase III trial), if the true OS rate at 2 years amounted to 45 % or more.
 
Probability to accept the experimental therapy as promising (> 45% OS rate) with respect to efficacy, in spite of a true OS rate of $\leq 40\%$: 5% (type I error).
 
Probability to reject the experimental therapy as not sufficiently efficient ($\leq 40\%$), although the true OS rate is promising (> 45%): 20% (type II error, corresponding to a power of 80%).
 
The final conclusion of this trial will depend on the definite OS rate (and its confidence interval), the respective findings in the 5-FU/cisplatin reference arm, as well as the information on type, frequency and severity of toxicities.

End of the study
	
The end of study is reached when the last patient has completed the 2-year Follow-up period.

[figure not shown]
Schedule of Assessments

Evaluation	Screening		Radio-immunochemotherapy				Follow-Up (every 3 month) ⁸
	Day -28 to 0	Day -7 to 0	weekly	every 4 weeks	after 4-4.5 weeks	End of Treatment	
Written informed consent	X						
Medical history	X						
Clinical staging (endoscopy incl. biopsy)	X				X	X	
Endoscopic ultrasound	X				X	X	X
Tumor assessment (CT chest, CT abdomen)	X				X	X	X
(Re)-evaluation by a surgeon with respect to resectability	X				X		

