7.3 End of Treatment Evaluations

After completion of the radio-immunochemotherapy or at the time of premature withdrawal for any reason the following assessments will be performed:

- Vital signs
- Karnofsky performance status
- Hematology (leucocytes, neutrophils, platelets, erythrocytes, hemoglobin)
- Clinical chemistry (sodium, potassium, calcium, magnesium, creatinine, bilirubin, , SGOT, SGPT, LDH, alkaline Phosphatase, γ -GT)
- Assessment of clinical signs or symptoms, toxicity according to NCI-CTC version 4.0
- Endoscopy (incl. biopsy, if patient agrees to participate in translational study)
- Endoscopic ultrasound (optional)
- Tumor Assessment (CT/MRI chest and abdomen)
serum sample (10 ml) for EGFR and ligands determination (if patient agrees to participate in translational study)

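### Loco-regional control is defined by endoscopy, EUS and CT, but follow-up requires only CT/MRI, so failures seen only, or earlier, by endoscopy or EUS are counted only in patients who happen to be examined

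*Combined protocol and SAP*

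**What the plan says.** **Endpoint.** Section 8.2.2 lists as a secondary variable "The 1-year and 2-year loco-regional control". The synopsis and section 8.3.1 define it: "Loco-regional control is defined as absence of loco-regional progression based on findings of endoscopy, endoscopic ultrasound, and computed tomography". Neither place says how the three methods combine, or what happens when one is missing. Section 8.3.1 estimates it "with the Kaplan-Meier method and measured from the day of randomization", and then: "Differences between the Kaplan-Meier curves are evaluated with the log-rank test", with significance at P < 0.05.

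**Endoscopy.** The schedule of assessments marks it at screening, after 4-4.5 weeks and at end of treatment, and leaves the follow-up cell empty. The follow-up lists in the synopsis and in section 7.4 do not contain it. The last listing is in section 7.3: "Endoscopy (incl. biopsy, if patient agrees to participate in translational study".

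**EUS.** In follow-up, both the synopsis and section 7.4 carry the entry "Endoscopic ultrasound (optional". The schedule table marks follow-up EUS without that qualifier.

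**Imaging.** CT/MRI of chest and abdomen is listed for follow-up with no optional label. Visits are every 3 months, starting 3 months after end of treatment. The definition of loco-regional control names CT but not MRI.

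**Blinding.** The trial is open-label (section 4.1). The text describes no central or blinded review of loco-regional progression.

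**The concern.** An endpoint defined by three methods needs all three applied alike in both arms up to the time it is read. Here both landmarks fall well after the last scheduled endoscopy. From then on, one of the defining methods is unscheduled and another is discretionary. Whether a patient has these examinations can depend on centre habit, on symptoms, and on a treating team that knows the allocation.

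Loco-regional control is also the secondary variable closest to the proposed mechanism: section 2.3.2.2 bases the combination on preclinical radiosensitisation. Section 8.3.3 justifies randomising partly because clinical evaluation will be handled alike in the two arms. For failures found only, or earlier, by endoscopy or EUS, the follow-up plan does not secure that. A difference in loco-regional control could then reflect who was examined, or a real difference could be blurred.

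**Working it through.** The plan gives no expected rate, event count or power for loco-regional control, so there is no figure to reproduce.

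**1. Time without scheduled endoscopy.** Planned treatment duration is 14 weeks (synopsis). Assume treatment starts at randomization, since the documents give no interval.
- Before the 1-year estimate: 52 − 14 = 38 weeks; 38/52 = 73%.
- Before the 2-year estimate: 104 − 14 = 90 weeks; 90/104 = 87%.

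A delay between randomization and treatment shortens the gap week for week. Early withdrawal brings the end-of-treatment evaluation forward and lengthens it.

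**2. What everyone does get.** Fourteen weeks is about 3.2 months. With 3-monthly visits, CT/MRI falls at about 6.2 and 9.2 months (2 scans before year 1), then 12.2, 15.2, 18.2 and 21.2 months (6 scans before year 2). Failures visible on CT/MRI are therefore sought systematically in both arms.

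**3. How large could the effect be?** Let F be the true share of patients failing loco-regionally after end of treatment, s the share of those failures visible only by endoscopy or EUS, and q the share of such patients who are examined. All three are assumptions; the documents give none of them.

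Observed control = 1 − F × (1 − s + s × q)

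With no true difference, the spurious difference between arms is F × s × (q₁ − q₂). With equal q, control is overstated in both arms by F × s × (1 − q).

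| Assumed examination shares | 1 year (F 20-35%, s 10-40%) | 2 years (F 30-50%, s 10-40%) |
|---|---|---|
| 50% vs 50%: difference | 0 | 0 |
| 50% vs 50%: overstatement in both arms | 1 to 7 points | 1.5 to 10 points |
| 70% vs 50%: difference | 0.4 to 2.8 points | 0.6 to 4.0 points |
| 90% vs 30%: difference | 1.2 to 8.4 points | 1.8 to 12.0 points |

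The largest entry, for example, is 0.50 × 0.40 × (0.90 − 0.30) = 0.12. These are upper-end values, because the formula never lets a missed luminal failure appear on a later scan.

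**4. Against sampling error.** Take F = 50%, s = 20% and q = 80% vs 40%. Observed failure is 40% + 8% = 48% against 40% + 4% = 44%, a spurious 4 points. With 36 per arm (a row of Table 10) and ignoring censoring, the standard error of the difference is √(0.48 × 0.52/36 + 0.44 × 0.56/36) = 0.117, or 11.7 points. The artefact is about one third of a standard error.

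**The case against.** **Most failures may be seen on CT/MRI.** This stands. It would be wrong to infer that the whole estimate depends on who is scoped. Three-monthly imaging is scheduled for all, so only failures seen solely, or earlier, by endoscopy or EUS are exposed.

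**The unequal examination shares are invented.** This also stands. Nothing in the documents supports a particular split. Variation between centres is not in itself variation between arms, because patients are randomized. An open label makes an imbalance possible, not established.

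**Endoscopy may be routine anyway.** Section 4.2.7 refers care after end of treatment to German Cancer Society guidelines, which are not available here, so neither routine endoscopy nor its absence can be asserted. Section 7.4 also has a misplaced phrase about optional biopsy, but it schedules no examination. What remains is that the protocol itself does not require endoscopy in follow-up.

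**A reader might infer that loco-regional control and progression-free survival contradict each other**, with an endoscopic recurrence failing the first but not the second. The documents do not show this. No section defines a progression-free survival event or ties it to RECIST. The relevant sentence in section 7.5.1, "If progression of disease is suspected for any reason during the treatment phase, radiological confirmation is necessary", is limited to the treatment phase. Counting biopsy-proven recurrences as progression-free survival events would also carry the same detection problem into that endpoint.

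**The endpoint is secondary and the trial exploratory.** True: section 8.3.3 disclaims a formal, rigorous comparison of arms. This limits the weight of the point. But section 8.3.1 still plans a log-rank comparison at P < 0.05, so how failures are detected still matters.

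**Conclusion.** The mismatch is documented: three methods define the endpoint, and only one is required of every patient after about week 14. Both the 1-year and 2-year estimates therefore rest partly on discretionary examinations in an open-label trial.

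The size and direction of any bias are unknown. The illustrative 2-year range, from no difference under equal examination to 12 points under an extreme split, depends wholly on the assumed F, s and q. Moderate imbalance gives effects that are small beside sampling error at this size. Even with equal examination, control would be somewhat overstated in both arms.

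The primary endpoint, 2-year overall survival, is not affected. The reading rests on the two text lists as well as the schedule table, so it does not depend on how the table was extracted. A low-cost improvement is justified; a conclusion that the endpoint is invalid is not.

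**What to change.** 1. Pre-specify an analysis of loco-regional control that, after end of treatment, counts only loco-regional progression on the scheduled CT/MRI. Report it beside the any-modality result for both arms. State how a patient with an endoscopic finding but no imaging progression is handled, and how events are dated.
2. Record for each event which method detected it and whether the examination was scheduled or symptom-driven, and tabulate this by arm.
3. Reconcile the schedule table with section 7.4 and the synopsis on whether follow-up EUS is optional, and the definition (CT) with the follow-up imaging (CT/MRI).

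The cost is one extra analysis and one CRF field for modality and trigger; no procedure is added. The drawback is that the CT/MRI-based version is less sensitive, so its control rates will look somewhat higher. For that reason it stands beside the three-method endpoint rather than replacing it, and the gap between the two shows how much depends on the discretionary examinations. Scheduling endoscopic assessment equally in both arms would also close the gap, but that is for the sponsor to weigh.
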